2.0 OBJECTIVES & ENDPOINTS

2.1 Primary Objective & Endpoint

The primary objective of this pilot study is to determine the safety profile of alisertib in patients with AMKL and in patients with MF.

Adverse events will be defined according to the National Cancer Institute's Common Terminology Criteria for Adverse Events (NCI CTCAE) version 4.0. The number, frequency, and severity of adverse events will be recorded every cycle for each population. All patients who receive at least 1 dose of alisertib will be considered evaluable for this endpoint.

2.2 Secondary Objectives & Endpoints

The secondary objective will be to determine preliminary efficacy of alisertib in both populations.

Serial blood and/or bone marrow samples will be collected at specific timepoints for each disease (see Section 5) to determine response to alisertib treatment. Responses will be categorized according to the revised/modified International Working Group (IWG) Response Criteria. Patients who had measurable disease at baseline, receive at least 1 cycle of treatment, and have at least one post-baseline disease assessment will be considered evaluable for this endpoint. Best response will be reported for all evaluable patients.

2.3 Exploratory Objectives & Endpoints

Exploratory objectives will include the following:

- 2.3.1 Describe pharmacodynamics (PD) effects of alisertib in peripheral blood and/or bone marrow samples.

Serial blood and/or bone marrow samples will be collected at specific timepoints. Flow cytometry, colony forming assays, AURKA autophosphorylation assays, and in vitro cultures of patient specimens to assess the effect of MLN8237 on megakaryocytes and other hematopoietic cells will be measured.

- 2.3.2 Evaluate the relationship between biomarker expression levels and response to alisertib.

Changes in biomarker expression levels from baseline will be measured (using PD samples) to correlate with response to alisertib therapy. Biomarkers will include a) genes encoding key enzymes in Aurora kinase signaling, b) markers of cellular aneuploidy and apoptosis, and c) markers of megakaryocytic differentiation.

- 2.3.3 Evaluate reduction in splenomegaly by palpation (MF arm only).

Patients will be examined for splenomegaly by palpation once per cycle and change from baseline will be calculated over time.

- 2.3.4 Evaluate improvement in MF symptoms (MF arm only), as assessed by the Myeloproliferative Neoplasm Symptom Assessment form (MPN-SAF).

The MPN-SAF will be administered to patients in the MF arm only once per cycle. Changes in symptom scores over time will be calculated.

- 2.3.5 Assess change in bone marrow fibrosis in patients in the MF arm. Bone marrow will be assessed at screening and after cycle 6 in this population.

3.0 PATIENT ELIGIBILITY

The target population for this study is patients with either AMKL or MF. This will be a multicenter trial conducted at Northwestern University, Miami University, and Mayo Clinic. Northwestern University will serve as the lead site and coordinating center for this study.

MF and AMKL are rare diseases with total prevalence (total number of patients with the disease in the US at any time) under 15,000. NIH considers prevalence under 200,000 a rare disease. A total of 24 subjects (maximum 24 subjects, regardless of the disease breakdown of MF or AMKL. If all 24 were MF, that would be acceptable) will be needed for this pilot trial. Approximately 4 potentially eligible patients are seen per month, and it is anticipated that at least 1 per month will be accrued (once all sites are up and running). Potential patients may be referred to the Principal Investigator (PI) at Northwestern University, [name] [contact] or [contact]), to [name] at Miami University, or to [name] at Mayo Clinic.

Eligibility will be evaluated according to the following criteria. Eligibility waivers are not permitted. Subjects must meet all of the inclusion and none of the exclusion criteria to be registered to the study. Study treatment may not begin until a subject is registered. Please refer to Section 11 for complete instructions regarding registration procedures.

3.1 Inclusion Criteria – AMKL Patients

- 3.1.1 Patients must have a confirmed diagnosis (by blood or bone marrow) of relapsed/refractory acute megakaryoblastic leukemia (AMKL), as defined by WHO criteria (see appendix I).
NOTE: If diagnosis was performed at an outside facility, a copy of the report is sufficient for registration purposes; however, local pathology review at one of the main sites should still be obtained.
- 3.1.2 Patients must be age 18 or older.
- 3.1.3 Patients must have an ECOG status 0-2.
- 3.1.4 Patients must exhibit adequate organ function within 1 week (7 days) prior to registration, defined as:
- Total bilirubin $\leq 1.5 \times$ ULN
 - ALT/AST $\leq 2.5 \times$ ULN
 - Creatinine $< 1.5 \times$ ULN or calculated creatinine clearance > 30 ml/min
 - PT and PTT $\leq 1.5 \times$ ULN
- 3.1.5 Patients must have estimated life expectancy of 6 months or greater.
- 3.1.6 Female patients of child-bearing potential (FOCBP) must have a negative serum beta-HCG pregnancy test within 7 days prior to registration.

NOTE: A FOCBP is *any woman* (regardless of sexual orientation, having undergone a tubal ligation, or remaining celibate by choice) who meets the following criteria:

- *Has not* undergone a hysterectomy or bilateral oophorectomy
 - *Has had* menses at any time in the preceding 12 consecutive months (and therefore has not been naturally postmenopausal for > 12 months)
- 3.1.7 Female patients must meet at least one of the following conditions:

- Must be post-menopausal for at least 1 year prior to registration (not of child-bearing potential as described above)
 - Must be surgically sterilized (as described above)
 - Willing to use an acceptable method of birth control (i.e. hormonal contraceptive, intra-uterine device, diaphragm with spermicide, condom with spermicide, or abstinence) for the duration of the study.
- 3.1.8 Male patients, even if surgically sterilized (i.e. status post-vasectomy) agrees to use an acceptable method for contraception during the entire study treatment period through 120 days after the last dose of alisertib. Likewise, female patients should agree to use acceptable method for contraception during the entire study treatment period through 90 days after the last dose of alisertib.
- 3.1.9 Patients must be able to understand and willing to sign a written informed consent.

3.2 Inclusion Criteria – MF Patients

- 3.2.1 Patients must have a confirmed diagnosis (by blood or bone marrow) of myelofibrosis (MF), as defined by WHO criteria (see appendix II).
NOTE: If diagnosis was performed an outside facility, a copy of the report is sufficient for registration purposes; however, local pathology review at one of the main sites should still be obtained.
- 3.2.2 Patients must be intermediate I risk or beyond and meet the following:
- in need of treatment;
 - intolerant or refractory to ruxolitinib (or other investigational JAK-inhibitors) OR unlikely to benefit from ruxolitinib
 - ineligible or refusal to undergo stem cell transplantation.
- 3.2.3 Patients must be age ≥ 18 years.
- 3.2.4 Patients must have an ECOG status 0-2.
- 3.2.5 Patients must have adequate bone marrow and organ function within 2 weeks (14 days prior to registration, defined as:
- Direct bilirubin $\leq 1.5 \times \text{ULN}$
 - ALT/AST $\leq 2.5 \times \text{ULN}$
 - Creatinine $< 1.5 \times \text{ULN}$ or calculated creatinine clearance $> 30 \text{ ml/min}$
 - PT and PTT $\leq 1.5 \times \text{ULN}$
 - ANC $\geq 1000/\text{mm}^3$
 - Platelets $\geq 50,000/\text{mm}^3$
- Note: this must be achieved without transfusion.
- 3.2.6 Patients must have estimated life expectancy of 6 months or greater.
- 3.2.7 Female patients of child-bearing potential (FOCBP) must have a negative serum beta-HCG pregnancy test within 7 days prior to registration.
NOTE: See section 3.1 for definition of FOCBP.
- 3.2.8 Female patients must meet at least one of the following conditions:
- Must be post-menopausal for at least 1 year prior to registration (not of child-bearing potential as described above)
 - Must be surgically sterilized (as described above)
 - Willing to use an acceptable method of birth control (i.e. hormonal contraceptive, intra-uterine device, diaphragm with spermicide, condom with spermicide, or abstinence) for the duration of the study.
- 3.2.9 Male patients, even if surgically sterilized (i.e. status post-vasectomy) agrees to use an acceptable method for contraception during the entire study treatment period through 120 days after the last dose of alisertib. Likewise, female patients should agree to use acceptable method for contraception during the entire study treatment period through 90 days after the last dose of alisertib.
- 3.2.10 Patients must be able to understand and willing to sign a written informed consent.

3.3 Exclusion Criteria – All Patients

- 3.3.1 Patients who have received treatment with clinically-significant enzyme inducers within 14 days prior to registration are not eligible. Please refer to Appendix III.
- 3.3.2 Patients who have received any investigational products, antineoplastic therapies, or radiotherapy within 14 days prior to registration are not eligible.
NOTE: Patients actively receiving hydroxyurea are eligible and may continue to receive hydroxyurea through cycle 1 of protocol treatment.. If the platelet count remains above 1 million after cycle 1, hydroxyurea can be used at the treating physician's discretion, if the platelets are $1000 \times 10^9/L$, or more, or if there are symptoms from thrombocytosis.
- 3.3.3 Patients who have received prior administration of an Aurora A kinase-targeted agent (including alisertib) are not eligible.
- 3.3.4 Patients who have received corticosteroids within 7 days prior registration are not eligible, UNLESS the patient has been taking a continuous dose of no more than 15 mg/day of prednisone for at least 1 month prior.
NOTE: Low dose steroid use for control of nausea and vomiting will be allowed. Topical steroid use and inhaled steroids are also permitted.
- 3.3.5 Patients who are candidates (eligible and willing) for standard and/or potentially curative treatments are not eligible.
- 3.3.6 Patients who have had major surgery within one month (28 days) prior to registration are not eligible.
- 3.3.7 Patients within 60 days of allogenic bone transplant are not eligible; patients with solid organ transplant are not eligible.
- 3.3.8 Patients who have had grade 2 or higher diarrhea, despite optimal anti-diarrheal supportive care, within 7 days prior to registration are not eligible.
- 3.3.9 Patients who have had grade 2 or higher peripheral neuropathy within 14 days prior to registration are not eligible (must have resolved to grade 1 or lower to register).
- 3.3.10 Patients who have had a myocardial infarction within 6 months (24 weeks) prior to registration are not eligible.
- 3.3.11 Patients who have class III or IV heart failure (as defined by the New York Heart Association), uncontrolled angina, severe uncontrolled ventricular arrhythmias, or electrocardiographic evidence of acute ischemia or active conduction system abnormalities are not eligible.
- 3.3.12 Patients who have known GI disease or GI procedures which could interfere with the oral absorption or tolerance of alisertib are not eligible. Examples include (but are not limited to) partial gastrectomy, history of small intestine surgery, and celiac disease.
- 3.3.13 Patients who have a known history of uncontrolled sleep apnea syndrome and other conditions that could result in excessive daytime sleepiness (such as severe chronic obstructive pulmonary disease or requirement for supplemental oxygen) are not eligible.
- 3.3.14 Patients who have a requirement for constant administration of proton pump inhibitor, H2 antagonist, or pancreatic enzymes are not eligible. Intermittent usage of antacids or H2 antagonists are allowed.
- 3.3.15 Patients with an active, uncontrolled systemic infection are not eligible until deemed controlled by the treating physician.
- 3.3.16 Patients who are known human immunodeficiency virus (HIV) positive are not eligible.
- 3.3.17 Patients who are known hepatitis B surface antigen-positive are not eligible.
- 3.3.18 Patients who have known or suspected active hepatitis C infections are not eligible.
NOTE: Patients who are hepatitis C surface antigen-positive are eligible.
- 3.3.19 Female patients who are pregnant or breast feeding are not eligible.

- 3.3.20 Patients who have any of the following severe acute or chronic medical or psychiatric conditions that may increase the risk associated with study participation or investigational product administration or may interfere with the interpretation of study results and, in the judgment of the investigator, would make the patient inappropriate for enrollment in this study are not eligible:
- uncontrolled diabetes
 - malabsorption
 - resection of the pancreas or upper small bowel
 - requirement for pancreatic enzymes
 - any condition that would modify small bowel absorption of oral medications,
 - other laboratory abnormality.
- 3.3.21 Patients who have symptomatic CNS involvement are not eligible.
- 3.3.22 Patients who have been diagnosed or treated for another malignancy within 3 years prior to registration are not eligible *aside from these exceptions*: completely resected basal cell carcinoma or squamous cell carcinoma of the skin, an in situ malignancy, or low-risk prostate cancer after curative therapy. If a patient had a prior MPN that evolved to a blast phase, but with treatment, reverted to Myelofibrosis at the time of screening, these pts are considered eligible at the discretion of the PI, if not considered suitable for stem cell transplantation.
- 3.3.23 Patients who are unable to swallow oral medication or are unwilling to comply with the administration requirements are not eligible.

4.0 TREATMENT PLAN

4.1 Overview

This will be a two arm pilot study of alisertib treatment in patients with AMKL or MF. The starting dose (level 1) for all patients will be 50 mg BID, administered orally on days 1-7 of each cycle (1 cycle = 21 days), based on the MTD from previous studies. Patients may continue to receive cycles of alisertib until progression of disease or unacceptable toxicity. There will be no long-term follow-up beyond end of treatment, aside from a standard end of treatment visit approximately 30 days after the last dose of study drug, followed by a final off-study visit approximately 6 months after the last dose. Patients with on-going adverse events will be followed until resolution of the event(s), defined as a return to baseline or stabilization of the event.

4.2 Treatment Administration

Alisertib will be administered orally BID on days 1-7 of each cycle; one cycle is defined as 21 days (days 8-21 will be rest days). Patients will be instructed to take each oral dose of alisertib with 8 ounces (1 cup, 240 mL) of water, with or without food. Doses on the same day should be taken approximately 12 hours apart (but *at least* 6 hours apart). All tablets are to be ingested whole; patients who have difficulty swallowing tablets will be excluded from the study. Antiemetic agents may be administered at the discretion of the investigator. Neutralizing antacids and calcium-containing supplements cannot be taken from 2 hours prior to alisertib dosing until up to 2 hours after dosing.

Patients will be dispensed the appropriate number of tablets required for each cycle. Treatment compliance will be assessed based on return of unused alisertib tablets and completion of a study medication diary; patients will be asked to bring completed diaries and pill bottles to each visit, and compliance will be reviewed by the study team each cycle. For MF patients only, from Cycle 1-6, on Day 1 of each cycle, when the patient comes in for clinic visit, they will be given study drug supply for one cycle (1 cycle=21 days). Beyond Cycle 6, if the patient's condition is stable, then they will be required to come in on Day 1 of every odd cycle (every 6 weeks) for study visit. In that case, patients will be given study drug supply for 2 cycles.

If a dose is missed due to patient error/oversight, they will be instructed to take the dose within 6 hours of the normal time. If more than 6 hours have elapsed, that missed dose should be omitted, and the patient should resume treatment at the next scheduled dosing time point. All missed/omitted doses and the reason will be reported on the diary. If a dose is vomited, it should not be re-taken. If a dose is held due to toxicity or investigator's discretion, the patient should be instructed to resume treatment at the investigator's discretion, taking into account all of the dose modification/discontinuation guidelines provided below.

From Cycle 1-6, in order for each new cycle of therapy to begin, MF patients must meet the following criteria: (if the cytopenias in AMKL patients are considered-disease related/due to AMKL then the following neutrophil and platelet count requirements do not apply. If cytopenias are considered due to the study drug, then the counts must be

- ANC must be $\geq 1000/\text{mm}^3$
- Platelet count must be $\geq 50,000/\text{mm}^3$
- In addition, all toxicities considered to be related to therapy with alisertib must have resolved to \leq Grade 1 or the patient's baseline values

For MF patients only, from Cycle 1-6 patients will be required to come in for study visit at beginning of every cycle (every 3 weeks). Beyond Cycle 6, if the patient's condition is stable, then they will be required to come in on Day 1 of every odd cycle (every 6 weeks) for study visit. In that case, for those visits when an MF patient is not coming to clinic for study visit, CBC and CMP will be done in an outside laboratory convenient for the patient, and results will have to be faxed to the clinic.

Patients can start their treatment at home only after the treating physician has reviewed the laboratory results and determined that they are able to continue treatment. For these cycles, the study coordinator will contact the patient on/prior to Day 1 to inform them if they can or cannot start the new cycle, and also check compliance regarding study drug intake.

4.3 Dose Modifications & Delays

Any patient who receives at least one dose of study therapy will be evaluable for toxicity endpoints. Each patient will be assessed for the development of toxicity according to the timeframe referenced in Section 5). Toxicity will be evaluated according to the NCI's CTCAE v 4. To manage excessive toxicity, reduction of the total alisertib dose can be done by reducing the daily dose administered and/or by interruption of the schedule treatment within a cycle.

In general treatment delays of up to 1 week for any reason are permitted. If a patient fails to meet the above-cited criteria for a new cycle of therapy, then initiation of the next cycle *should be delayed* for up to 1 week. At the end of that week, the patient should be re-evaluated to determine whether the criteria for retreatment have been met. Should treatment need to be delayed for more than 1 week because of incomplete recovery from treatment-related toxicity, the dose of alisertib will be reduced (see table below) to 40 mg BID when therapy resumes. A second dose reduction to 30 mg BID may occur should treatment need to be delayed for more than 1 week because of incomplete recovery from treatment-related toxicity at the 40 mg BID dose. Patients who require further dose reduction will be removed from the study. Should treatment need to be delayed for more than 2 weeks at any dose, therapy with alisertib will be discontinued.

Dose Level	Alisertib¹
Level 1 (starting dose)	50 mg
Level -1	40 mg
Level -2	30 mg
Level -3	Discontinue

¹ Doses are administered orally, BID on days 1-7 of each cycle.

4.3.1 **Dose Modifications for Hematological Toxicities**

If a patient experiences any of the following hematological toxicities during the dosing period, dosing will be discontinued for the remainder of that cycle and the dose will be decreased by 1 level (-10 mg) for all subsequent cycles of treatment.

- Grade 4 neutropenia (ANC < 500 cells/mm³) lasting more than 7 consecutive days
- Grade 4 thrombocytopenia (platelet count < 25,000/ μ L) lasting more than 7 consecutive days
- Platelet count less than 10,000/ μ L at any time
- Grade 3 neutropenia with fever or infection, or both, where fever is defined as an oral temperature greater than 38.5°C
- Grade 3 thrombocytopenia with clinically significant bleeding

4.3.2 **Dose Modifications for Non-hematological Toxicities**

If a patient experiences any of the following toxicities during the dosing period, dosing will be held for the remainder of that cycle and the dose will be decreased by 1 level (-10 mg) for all subsequent cycles of treatment, and treatment may resume after drug related toxicities have resolved to \leq Grade 1 or to baseline.

- Any Grade 3 non-hematological toxicity that is considered by the investigator to be related to study drug other than:
 - Grade 3 or greater nausea or emesis, or both, that occurs in the absence of optimal antiemetic therapy (5-hydroxytryptamine 3 [5-HT₃] serotonin receptor antagonist);
 - Grade 3 or greater diarrhea that occurs in the absence of optimal supportive therapy with loperamide or a comparable anti-diarrheal;
 - Grade 3 fatigue that lasts less than 1 week
- Grade 2 non-hematological toxicities that are considered by the investigator to be related to study drug and in the opinion of the investigator require dose reduction.
- Any grade 4 non-hematological toxicity that is considered by the investigator to be related to study drug. If, in the opinion of the investigator and the DMC, it is in the patient's interest to continue therapy with alisertib, the patient may resume therapy after recovery from a grade 4 to \leq Grade 1 or to baseline values; the dose of alisertib should be reduced by at least 1 dose level for subsequent cycles of therapy.

When intra-patient dose reduction of alisertib is required, no re-escalation of dose will be permitted. If a patient requires more than 2 dose reductions, therapy with alisertib will be discontinued.

4.4 **Management of Clinical Events**

4.4.1 **Nausea and vomiting**

Prophylactic antiemetic therapy will not be used in this study unless it becomes clear that alisertib causes acute nausea and vomiting. Although this study will not initially employ prophylactic antiemetics, there is no prohibition against antiemetic use in the management of a patient who develops nausea or vomiting, or both. If

prophylactic antiemetic therapy is needed, 5 HT3 receptor antagonists (without corticosteroids) should be tried first. Because of the potential of benzodiazepines to cause sedation, the use of benzodiazepines for antiemetic prophylaxis should be reserved for patients who cannot be satisfactorily managed otherwise.

4.4.2 **Diarrhea**

Antidiarrheal medications will not be used prophylactically; however, patients will be instructed to take loperamide, 4 mg, at the occurrence of the first loose stool and then 2 mg every 2 hours until they are diarrhea-free for at least 12 hours. During the night, patients may take 4 mg of loperamide every 4 hours. Fluid intake should be maintained to avoid dehydration.

4.4.3 **Central nervous system effects**

If a patient experiences excessive sedation believed to be related to alisertib, treatment with alisertib should be interrupted. Patients whose sedation is not considered immediately life-threatening should be carefully monitored and given appropriate supportive care. Patients and family members/caregivers will be explicitly counseled regarding the possibility for sedation during the informed consent process, prior to cycle 1, and with each study visit/AE assessment. Patients and family members/caregivers will be counseled not to drive, operate heavy or dangerous machinery, or perform any other dangerous activities if they experience any sedation with alisertib.

If the patient's level of consciousness is considered to be life-threatening, necessary measures should be instituted to secure the airway, ventilation, and intravenous access. Flumazenil (Romazicon®) is a selective benzodiazepine receptor antagonist that is intended as an adjunct to, not as a substitute for, the proper management of benzodiazepine overdose. Although there is neither preclinical nor clinical experience with flumazenil and alisertib, the use of flumazenil should be considered if the level of alisertib-associated sedation is considered to be life-threatening. Patients treated with flumazenil should be monitored for re-sedation, respiratory depression, and other residual benzodiazepine effects for an appropriate period after treatment. Continued monitoring is particularly important in the case of alisertib given its half-life and the comparatively brief half-life of flumazenil in the CNS (20-30 minutes). Flumazenil should be administered according to its label.

4.4.4 **Differentiation syndrome**

In this study, alisertib is being used as a differentiation agent in the treatment of AMKL and MF, and theoretically, there exists a possibility for a unique differentiation syndrome as can be seen with acute promyelocytic leukemia when using differentiation therapy. Therefore, patients will be monitored for symptoms of a differentiation syndrome. Taking from the experience in APL, patients will be monitored for the following symptoms or signs: fever, peripheral edema, hypoxemia, respiratory distress, hypotension, renal and hepatic dysfunction, and serositis (shortness of breath, pleurisy, abdominal distension). The study team will be counseled about the presenting features of this acute illness. With regard to the monitoring plan, with suspected differentiation syndrome, alisertib will be held. Patients will require hospitalization for careful monitoring and observation. Supportive care maneuvers will include supplemental oxygen for those with hypoxia, In severe cases, ventilatory support will be required. In the presence of volume overload, if hemodynamics permit, diuresis can be attempted. Those with dyspnea or abdominal discomfort will require imaging to evaluate for the presence of effusion, pulmonary opacity, and ascites. Patients will be assessed for the presence of coagulopathy, and if present, supportive care with fresh frozen plasma, platelet transfusions, or

cryoprecipitate will be considered. Intravenous dexamethasone (10mg IV q12 hours x 3 days) will be administered in those with differentiation syndrome.

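### Section 4.3.1 ties its hematological dose-reduction triggers to an undefined dosing period; read as days 1-7, the two triggers needing more than 7 days of Grade 4 counts cannot be met by a patient outside Grade 4 on Day 1.

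*Combined protocol and SAP*

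**What the plan says.** Section 4.3.1 lists five triggers. It applies them to "hematological toxicities during the dosing period, dosing will be discontinued for the remainder of that cycle", and the dose then falls one level for all later cycles. Two of the five, Grade 4 neutropenia (ANC below 500/mm³) and Grade 4 thrombocytopenia (platelets below 25,000/µL), count only when "lasting more than 7 consecutive days". The other three have no duration requirement.

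The protocol does not define the dosing period. Section 4.2 states "one cycle is defined as 21 days (days 8-21 will be rest days", and the footnote to the dose table in 4.3 repeats "Doses are administered orally, BID on days 1-7 of each cycle".

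Three other rules bear on the point:

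- **Restart criteria (4.2).** "From Cycle 1-6, in order for each new cycle of therapy to begin, MF patients must meet the following criteria": ANC at least 1000/mm³, platelets at least 50,000/mm³, and alisertib-related toxicities back to Grade 1 or lower, or to baseline. AMKL patients whose cytopenias are judged disease-related are exempt from the two count criteria.
- **Delay rule (4.3).** "In general treatment delays of up to 1 week for any reason are permitted". A reduction is mandatory only in this case: "Should treatment need to be delayed for more than 1 week because of incomplete recovery from treatment-related toxicity".
- **General discretion (4.3).** "To manage excessive toxicity, reduction of the total alisertib dose can be done by reducing the daily dose administered".

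**The concern.** The window named in 4.3.1 is 7 days long if it means the days on which drug is taken, while two triggers inside it need more than 7 days. The stated consequence, stopping dosing for the rest of the cycle, presupposes that dosing is still under way, which supports the days 1-7 reading.

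What is at stake is patient safety. Safety is the primary objective, myelosuppression is the first risk listed in section 1.5.2, and section 1.6 says that disturbed hematopoiesis in these patients raises the risk of toxicity. Someone with more than 7 days of drug-induced Grade 4 cytopenia who recovers in time and meets no other trigger could restart at the same dose. The two duration triggers were presumably listed to make that reduction mandatory. Different sites could also handle the same event differently.

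**Working it through.** The plan gives no figure on this point, so the check is a day count.

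**Inputs.** Dosing on days 1-7 of a 21-day cycle (4.2, 4.3). More than 7 consecutive days taken as at least 8 calendar days (4.3.1). Day 1 floors of 1000 and 50,000, both outside Grade 4 (4.2). Permitted delay of 1 week (4.3). Required hematology on days 1, 4, 8 and 15 of cycle 1, days 1 and 15 of cycles 2-6, and day 1 afterwards (5.1 and 5.2, footnote e).

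**1. Can the trigger be met by Day 7?** Let s be the first Grade 4 day.

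- Run length by the end of Day 7 = 7 − s + 1.
- s = 2 gives 6 days. Counting an onset later on Day 1 gives 7. Neither exceeds 7.
- The 8th day is s + 7, so with onset on Day 2 it is Day 9.

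**2. Patterns inside one cycle.** Let e be the last Grade 4 day, with s ≥ 2, e ≤ 21 and e − s + 1 ≥ 8. Each s from 2 to 14 has 15 − s possible ends: 13 + 12 + … + 1 = 91.

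| Reading of the window | Patterns meeting the trigger |
|---|---|
| 8th day falls within days 1-7 | 0 of 91 |
| Onset on days 2-7 is enough | 13 + 12 + 11 + 10 + 9 + 8 = 63 of 91 |
| Any day up to the next cycle | 91 of 91 |

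If full recovery comes k days after e, restart by Day 29 (planned Day 22 plus 7) needs e + k ≤ 29. With e ≤ 21, all 91 escape the delay rule for any k up to 8.

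**3. Patterns ending on Day 22 or later.** For each e there are e − 8 onsets, and restart without a mandated reduction needs e ≤ 29 − k. The documents do not give k, so it is an assumption:

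- k = 1: 14 + 15 + 16 + 17 + 18 + 19 + 20 = 119
- k = 3: 14 + 15 + 16 + 17 + 18 = 80
- k = 7: 14

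**4. Can required labs show the duration?** This uses nominal days and two Grade 4 counts.

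- Cycle 1, e ≤ 21: days 8 and 15 span 8 calendar days but only 7 elapsed days. Counting calendar days, s ≤ 8 and e ≥ 15 gives 7 × 7 = 49 of 91. Requiring more than 7 elapsed days needs days 4 and 15: 3 × 7 = 21 of 91.
- Cycles 2-6 and cycle 7 onward, e ≤ 21: 0 of 91, because there is at most one draw after Day 1.
- Delayed recovery in cycles 2-6: Day 15 and the planned next Day 1 (Day 22) span 8 calendar days but exactly 7 elapsed days, so the duration is shown only on the calendar-day count.

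**5. Exceptions.**

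- An exempt AMKL patient can enter Day 1 already at Grade 4, so a run that began earlier can pass 7 days inside the window.
- Footnote e allows ±2 days for draws. With a count drawn two days before Day 1, Grade 4 onset the next day gives 8 days by Day 7, and onset the same day gives 9. With a count drawn one day early, the figures are 7 and 8.

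**The case against.** The strongest reply is that days 1-7 is only one reading of an undefined term, and that an investigator would choose a reading that gives every trigger effect. The platelet trigger below 10,000/µL, which applies whenever it occurs, hints at a wider intent. This stands as far as it goes: the defect is one of wording. It does not settle which reading applies. Counting by onset on days 2-7 still leaves 28 of the 91 patterns without a mandated reduction, and section 11.5 asks for the study to be run exactly as the protocol describes.

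A second reply is that other safeguards exist: the restart criteria, the delay rule, discretion to reduce, follow-up of abnormal labs (7.1) and DMC review. These do limit the harm. A reader might infer that patients could be re-dosed while still severely cytopenic. The documents do not support that for anyone held to the start counts, because leaving Grade 4 is not enough and all three restart criteria must be met. But those criteria govern when treatment resumes, not at what dose, and the delay rule mandates a reduction only beyond one week.

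A reader might also infer that all 119 late-ending patterns escape a mandated reduction. That figure is a ceiling: it assumes full recovery the day after the last Grade 4 count.

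**Conclusion.** The point holds as a wording defect in a safety rule, and it is worth correcting. On the natural reading, a patient outside Grade 4 on Day 1 itself cannot meet either duration trigger. The trigger is met in 0 of 91 within-cycle patterns, against 91 of 91 if the whole cycle counts. A further 14 to 119 patterns ending on Day 22 or later are affected, for assumed recovery lags of 7 days down to 1.

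The conclusion rests on reading the dosing period as days 1-7 and on counts being adequate on Day 1. It does not cover exempt AMKL patients or counts drawn early. The start counts are written for cycles 1-6; home-start cycles for stable MF patients after that rest on physician review of labs.

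Two further inferences go too far. One is that the pattern counts measure how often this would happen; they are unweighted, and the documents give no frequency. The other is that the trial's results or precision are affected; no statistical figure changes.

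**What to change.** In 4.3.1, replace the dosing-period phrase with *at any time during the cycle, up to the start of the next cycle*, for all five triggers. Any doses left in that cycle are stopped, and the dose falls one level for subsequent cycles. Make the same change to the matching phrase in 4.3.2. Widening only the two duration triggers would imply that the other three stop at Day 7, so that febrile Grade 3 neutropenia on a rest day, for example, would mandate nothing.

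For the duration triggers, the 8th day falls on Day 9 or later when onset is Day 2 or later. Only the reduction for later cycles then has practical effect.

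The cost is one phrase in each of two subsections, with no added visits or labs, and possibly a few more dose reductions. One limit should be stated in the protocol: after cycle 1, the required labs cannot document more than 7 days in a patient who met the Day 1 counts and recovers by the next Day 1. The benefit there depends on unscheduled labs, which the schedules of events already allow at the investigator's discretion.
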